### **Background:**

Traumatic brain injury (TBI) is a global pandemic that affects over 10 million people annually, with the incidence expected to continue to mushroom in coming years (1). In industrialized nations, this is a trivial requirement, as CT scans are used ubiquitously to definitively diagnose epidural hematomas (EPH) and subdural hematomas (SDH), readily and reliably triaging patients to surgical versus medical management. In less developed countries, CT scanners are often nonexistent. When they are present, they are extremely meager in number, peppered across treacherous geography, with scant transportation and emergency infrastructure.

In 1997, the first ever handheld device that could definitively detect the presence and location of epidural and subdural hematomas was introduced (2). Initially named the Runman, the device was intended to detect intracranial hematomas in remote and military settings to triage which casualties should be airlifted to medical centers equipped to offer neurosurgery. After numerous iterations, the InfraScanner 1000™ was introduced in the mid 2000's. In 2010, the pivotal five-site double-blinded clinical trial was published, and ultimately led to FDA clearance of the InfraScanner 1000™. In the study, the Infrascanner 1000™ measurements were compared to CT scans of 365 patients, 96 of which were hematoma cases of various sizes, depths and locations. The study demonstrated high sensitivity (88%) in detecting hematomas > 3.5cc in volume and < 2.5 cm from the surface of the brain, and a specificity of 91%. Since then there have been numerous studies that have replicated these results and have substantiated that it is a capable tool for pre-hospital diagnosis of intracranial hematomas (2-12).

The goal of this study is to determine the sensitivity, specificity, and positive and negative predictive values of the portable near-infrared-based device (portable NIR-based device), the InfraScanner 2000™, to detect intracranial hematomas [EDH and/or SDH] in patients hospitalized at Duke University Hospital (DUH) who have sustained or who are suspected to have sustained head trauma and have consequently received a brain computed tomography (CT) scan(s).

### **Specific Aims:**

**Aim 1:** Determine whether the InfraScanner 2000™ detects epidural and/or subdural hematomas with adequate precision relative to CT scans to be used as a diagnostic tool for epidural and/or subdural hematomas.

**Aim 2:** Use these findings to inform the feasibility of conducting a future trial in which the InfraScanner 2000™ is used as a stand-alone diagnostic tool for intracranial hematomas, and therein, to determine candidacy for decompressive craniotomies in patients who suffer traumatic brain injuries in places where CT scans are not available.

**Primary Objective:**

1. Estimate the test characteristics (sensitivity, specificity, and the false positive and false negative rates) of the portable NIR-based device (InfraScanner 2000™) in the identification of any size hematoma. The results of the CT scan(s) will serve as the gold standard.

**Secondary Objective:**

1. Estimate the test characteristics of the InfraScanner 2000™ in identification of hematomas within its detection limits (volume >3.5 mL and depth <2.5 cm) compared to CT scan results as the gold standard.

**Study Population:**

- Any patient who presents to DUH with suspected head trauma and receives a brain CT scan will be considered for this study. Our final sample size is 581 measurements for 500 patients.

**Inclusion/Exclusion:**

- Duke ER patient with suspected head trauma and received a brain CT scan

**Data Management:**

**Explain multiple measurements for the same patients,  
Sample size**

If there are multiple scans on a single patient, define the presence of a hematoma per patient as the first hematoma detected by the Infrascanner on any assessment and compare results with the corresponding CT assessment (within 30 minutes on same date).

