### **Statistical Analysis:**

#### **Definitions of the statistics of interest:**

Let A+ denote the event that the test is positive for hematoma and B+ denote the event that a hematoma is present. Sensitivity,  $P(A+/B+)$ , will be defined for each patient (scan) as the probability that a true hematoma as determined by CT scan will be detected (14). Similarly, let A- denote the event that the test is negative for hematoma and B- denote the event that a hematoma is not present. Specificity,  $P(A-/B-)$ , will be defined as the probability of being negative for hematoma on the InfraScanner 2000™ scan within 30 minutes of CT given the patient has no hematoma present.

The false positive rate will be defined as  $PF+ = P(B-/A+) = P(A+/B-)[1-P(B+)]/P(A+)$ . Similarly, the false negative rate will be defined as  $PF- = P(B+/A-) = [1-P(A+/B+)]P(B+)/[1-P(A+)]$ . Estimates for the false positive and false negative rates will be provided for a range of values for the prevalence of hematomas.

1. Estimation of test characteristics with 90% confidence at the patient level using SAS 9.4;
2. Estimate test characteristics at the scan level (treat each measurement as independent sample) and 95% confidence intervals will be computed as a secondary analysis.
3. Estimating Receiver Operating Characteristic (ROC) curves with patient and scan as the units of analysis with 95% confidence interval.
4. Fit a logistics regression of correct and incorrect detection from InfraScanner, adjusting for age, gender, skin color, hair color, hair thickness, hair length, scalp hematoma, scalp laceration, scalp fracture, ventricular effacement and midline shift.

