#### **Analysis plan:**

1. A baseline table (Table 1) will describe overall study cohort characteristics by hematoma status.
2. Hematoma characteristics will be summarized at the patient level and also at the scan level (Table 2 and Table 3).
3. A 2x2 table of CT and InfraScanner results. Sensitivity, specificity, false positive value, false negative value, and their 95% confidence intervals will be calculated at patient level using the contingency table and reported. Repeat the analysis at scan level.
4. 2x2 tables of CT and InfraScanner results by quadrant. Corresponding counts and test characteristics will be calculated for each quadrant (frontal, temporal, parietal, and occipital). Repeat the analysis at scan level.
5. 2x2 tables of CT and InfraScanner results for hematomas within the detection limit. Corresponding counts and test characteristics will be calculated for hematomas within the detection limit (blood volume > 3.5 cc and distance from cranium < 2.5 cm). Repeat the analysis at scan level.

6. 2x2 tables of CT and InfraScanner results by types of hematoma. Corresponding counts and test characteristics will be calculated for each type of hematoma (SDH, EDH, etc.). Repeat the analysis at scan level.
7. 2x2 tables of CT and InfraScanner results by types of hematoma for those within the detection limit. Corresponding counts and test characteristics will be calculated for each type of hematoma (SDH, EDH, etc.) for those within the detection limit (blood volume > 3.5 cc and distance from cranium < 2.5 cm). Repeat the analysis at scan level.
8. Minimum blood volume detected as positive by InfraScanner 2000 will be reported.
9. Distributions of Blood Volumes and Difference in Optical Density ( $\Delta OD$ ) will be plotted for patients with hematoma.
10. InfraScanner results for special cases will be reported. Special cases include: patients who died, or had surgeries (craniectomy or craniotomy), or had ventricular effacement or midline shift.
11. Logistic regression model will be fit to assess the association between InfraScanner result and potential confounders that include patient age, sex, hair length, hair thickness, hair color, skin color, scalp laceration, scalp fracture, and scalp hematoma. Odds ratios with 95% CI will be reported.

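### For patients with repeat scans, the patient-level rule lets the InfraScanner result choose which CT/device pair is scored, and it names no pair when every device scan is negative

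*SAP*

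**What the plan says.** The SAP has one rule for reducing several scans to a single patient-level result. Under Data Management it tells the analyst to "define the presence of a hematoma per patient as the first hematoma detected by the Infrascanner on any assessment" and then to "compare results with the corresponding CT assessment (within 30 minutes on same date").

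Everywhere else CT is the reference. The SAP's Primary Objective states: "The results of the CT scan(s) will serve as the gold standard". The definitions under Statistical Analysis describe sensitivity "as the probability that a true hematoma as determined by CT scan will be detected", and tie specificity to the device scan taken close in time to a CT without hematoma.

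The SAP's list of analyses opens with "Estimation of test characteristics with 90% confidence at the patient level using SAS 9.4". Its second item is "Estimate test characteristics at the scan level (treat each measurement as independent sample"), which it calls secondary. In the Analysis plan, item 3, the 2x2 statistics "will be calculated at patient level using the contingency table and reported", and are then repeated by scan. Protocol section 13 places both levels under the primary objective and bases the sample size on the number of patients with hematoma. Neither document gives another way to combine serial scans.

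On the number of repeats, the SAP's Study Population section says: "Our final sample size is 581 measurements for 500 patients". Protocol section 13 had expected about 90% of patients to have more than one CT.

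**The concern.** In an accuracy study, the observation to be scored should be chosen without looking at the index test. Here the first positive InfraScanner scan selects the pair, and so also selects the CT that supplies the truth for that patient.

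- **CT unchanged between scans.** Any positive device scan makes the patient device-positive. A CT-positive patient missed first and detected later is scored as a true positive, so the miss disappears from the patient-level table. A CT-negative patient gets a further chance of a false positive with each rescan.
- **CT changes between scans.** The device result now decides whether the patient counts as CT-positive or CT-negative. Protocol section 2 notes that serial CT can show a bleed evolving or resolving, and section 4 allows collection for up to 30 days, so such changes are possible.
- **All device scans negative.** The rule selects no pair. For the 2x2 table this is harmless if the patient's CTs agree. If they differ, the analyst's choice decides between a false negative and a true negative.

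At stake is the patient-level 2x2 table, which the SAP lists first and on which the trial was sized.

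**Working it through.** **1. The plan's own figures.** With 68 hematoma patients, the 90% half-width at p = 0.5 is 1.645 × √(0.25/68) = 0.0997 (Protocol section 13 states 0.099). At 13% prevalence, 68/0.13 = 523 patients, as stated. At the final 500 patients, 13% gives 65 CT-positive and 435 CT-negative patients.

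**2. How many patients the rule can reach.** 581 − 500 = 81 repeat measurements, so at most 81 patients (81/500 = 16.2%) have more than one and at least 419 have exactly one.

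**3. Assumptions.** The documents do not give repeats by CT status. I take two scans per rescanned patient and an even spread: 81 × 0.13 = 10.5, so about 11 CT-positive and 70 CT-negative patients rescanned. As an alternative, 20 of the 65 CT-positive patients are rescanned. Per-scan sensitivity p is 0.75 to 0.88 and specificity 0.91. The 0.88 and 0.91 are the results quoted for the earlier device model, and the 0.88 applies within detection limits; 0.75 is an assumed lower value for hematomas of any size. Within-patient correlation ρ is 0 to 0.9.

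**4. CT unchanged: sensitivity.** Compared with scoring the first pair, a CT-positive patient changes cell only if the device is negative first and positive second, which has probability p(1−p)(1−ρ). With k of 65 rescanned, the shift is (k/65) × p(1−p)(1−ρ). At k = 11, p = 0.75 and ρ = 0 it is (11/65) × 0.1875 = 3.17 points.

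| k | p | ρ = 0 | ρ = 0.6 | ρ = 0.9 |
|---|---|---|---|---|
| 11 | 0.75 | 3.17 | 1.27 | 0.32 |
| 11 | 0.88 | 1.79 | 0.71 | 0.18 |
| 20 | 0.75 | 5.77 | 2.31 | 0.58 |
| 20 | 0.88 | 3.25 | 1.30 | 0.32 |

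(Upward shift in sensitivity, percentage points.)

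**5. Against sampling error.** The 90% half-width is 1.645 × √(p(1−p)/65) = 8.84 points at 0.75 and 6.63 at 0.88. Even at ρ = 0, the shift equals the half-width only when k reaches 30.6 (at 0.75) or 40.8 (at 0.88) of the 65.

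**6. CT unchanged: the other measures, even spread.** Specificity falls by (70/435) × 0.91 × 0.09 × (1−ρ) = 1.32, 0.53 and 0.13 points at ρ = 0, 0.6 and 0.9. At 13% prevalence the SAP's false positive rate, P(B−|A+), goes from 0.445 to 0.469, 0.455 and 0.448 (p = 0.75), or from 0.406 to 0.435, 0.418 and 0.409 (p = 0.88). Its false negative rate, P(B+|A−), falls by 0.43, 0.17 and 0.04 points, or 0.26, 0.10 and 0.03 points.

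**7. CT changes, two scans.** The probabilities assume independent results. The number of such patients is not given.

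| CT sequence | Device sequence | Scored as | Probability |
|---|---|---|---|
| − then + | + then anything | false positive | 0.09 |
| − then + | − then + | true positive | 0.91 × p = 0.68 to 0.80 |
| + then − | + then anything | true positive | p = 0.75 to 0.88 |
| + then − | − then + | false positive, and out of the sensitivity denominator | (1−p) × 0.09 = 0.011 to 0.023 |
| either | − then − | no pair named | (1−p) × 0.91 = 0.109 to 0.228 |

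To show what the last row can do: with 65 CT-positive patients and 57.2 detected (0.880), moving one such patient from false negative to true negative gives 57.2/64 = 0.894.

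**The case against.** The strongest reply is that the rule describes a legitimate target: whether the device ever detects the hematoma over repeated use. Protocol sections 2 and 3 do envisage repeated, sequential scanning, and the SAP's definition of sensitivity does not say on which scan detection must occur. On that view the rise is not inflation. This does not rescue the rule. An ever-detected measure needs a patient-level CT status across all scans, and the SAP gives none. Rescans also follow clinical CTs, not a schedule, so the number of chances to detect varies between patients for reasons unrelated to the device.

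The reply on size is fair. With CT unchanged, even spread and independent repeats, the patients whose cell actually differs number 11 × 0.1875 = 2.1 (or 11 × 0.1056 = 1.2) CT-positive plus 70 × 0.0819 = 5.7 CT-negative. That is about 7 to 8 of 500, and fewer than 1 at ρ = 0.9. The shift does not uniformly favour the device, because specificity falls. The study is a pilot with estimation aims and no success threshold to cross. The scan-level tables keep every miss visible, although the SAP calls that analysis secondary.

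It is also true that the first pair is not the only sound choice. The first CT-positive pair, or the first pair if there is none, would also be independent of the device and would retain hematomas that appear later.

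**Conclusion.** The concern holds and should be fixed. That the index test selects the pair, and that all-negative patients have no named pair, follows from the SAP's wording and is not cured elsewhere in either document. The direction under unchanged CT is certain; the size is not.

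With an even spread of repeats, sensitivity is overstated by 0.7 to 3.2 points for correlation 0 to 0.6, and by 0.2 to 0.3 at 0.9. If 20 of 65 CT-positive patients were rescanned, the figures are 1.3 to 5.8 and 0.3 to 0.6. With the even spread, specificity is understated by 0.1 to 1.3 points, P(B−|A+) rises by 0.3 to 2.8 points and P(B+|A−) falls by 0.03 to 0.4 points. These sensitivity shifts are smaller than the sampling half-width, but they are avoidable bias that the confidence interval does not reflect. They rest on assumed accuracy, correlation, number of scans per patient and split of repeats. The effect of changing CT status cannot be sized, because no count of such patients is given.

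**What to change.** Replace the Data Management rule with: *The patient-level analysis uses each patient's first paired CT/InfraScanner measurement; CT on that pair defines hematoma present or absent, whatever the InfraScanner result.* Keep all later pairs in the scan-level analysis, and state that the change was made after enrolment. This defines a pair for every patient, including those whose device scans are all negative.

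The cost is one SAP sentence, the note on timing, and a re-run of the patient-level tables on data already held. The downside is that a patient who is CT-negative first and CT-positive later counts as CT-negative at patient level, so hematomas first seen on a later scan appear only at scan level. That may slightly reduce the number of CT-positive patients (about 65 assumed, against 68 planned).

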**Variables:**

1. Age: continuous
2. Sex: male/female
3. Skin color: white/light brown/dark brown/black/yellow
4. Hair thickness: bald/thin/medium/thick/MPB
5. Hair color: NA/white/grey/blond/light brown/dark brown/black/red
6. Hair length: bald/0-1 inch/1-3 inches/3-6 inches/>6 inches
7. Scalp hematoma present: Y/N, if yes, Y/N at 8 different locations (left/right frontal/temporal/parietal/occipital)
8. Scalp laceration present: Y/N, if yes, Y/N at 8 different locations (left/right frontal/temporal/parietal/occipital)
9. Scalp fracture present: Y/N, if yes, Y/N at 8 different locations (left/right frontal/temporal/parietal/occipital)

10. Positive infrascan: Y/N
11. Positive CT: Y/N, if yes, Y/N at 8 different locations (left/right frontal/temporal/parietal/occipital)
12. Ventricular effacement: Y/N
13. Midline shift: Y/N
14. CT blood location: Y/N, if yes, Y/N at 8 different locations (left/right frontal/temporal/parietal/occipital)
15. CT blood size: in cubic centimeters (cc) at 8 different locations (left/right frontal/temporal/parietal/occipital)
16. Distance-from-cranium: TBD

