10. Device Description/Mechanism: The following description is adapted from the InfraScanner White Paper (20): All biological tissue is, to differing extent, permeable to electromagnetic radiation of different frequencies and intensities. This can also be considered permeability to photons of different energy levels. This permeability to electromagnetic energy is the basis of all imaging based on transmission/scattering characteristics such x-ray, Computed Tomography, and near-infrared, NIR, imaging. From the principles of spectroscopy, it is also known that different molecules absorb different wavelengths of electromagnetic radiation (which is synonymously referred to as light at shorter wavelengths). Similarly, tissue scatters radiation to different degrees. The Infrascanner is concerned with NIR imaging of the hemoglobin molecules. From any light source, photons follow a characteristic path through the target tissue back to a detector on the same approximate plane as the source. While the light is severely attenuated due to the scattering and absorption process, it is nonetheless encoded with the spectroscopic signatures of the molecules encountered en route to the detector (Image C).

The principle used in identifying intracranial hematomas with the Infrascanner is that extravascular blood absorbs NIR light more than intravascular blood. This is because there is a greater (usually 10-fold) concentration of hemoglobin in an acute hematoma than in normal brain tissue where blood is contained within vessels. The Infrascanner compares left and right side of the brain in four different areas. The absorbance of NIR light is greater (and therefore the reflected light less) on the side of the brain containing a hematoma, than on the uninjured side. With specified wavelength ranges, optical light source(s) or emitter(s) and a photodetector are placed at a distance, which allows proper NIRS absorption measurements in a desired volume of tissue. The wavelength of 805nm is sensitive only to blood volume, not to oxygen saturation in the blood (Image D).

The Infrascanner is placed successively in the left and right frontal (F), temporal (T), parietal (P), and occipital (O) areas of the head and the absorbance of light is recorded. Specifically the placement is as follows:

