Frontal Left/Right forehead, above the frontal sinus; Temporal In the Left/Right temporal fossa; Parietal Above the Left/Right ear, midway between the ear and the midline of the skull; Occipital Behind the Left/Right ear, midway between the ear and the occipital protuberance (Image B).

The difference in optical density (ΔOD) in each of the four symmetrical areas is calculated on a pair-wise basis from the following formula:

$$\Delta OD = \log_{10} \left(\frac{I_N}{I_H} \right) = \log_{10}(I_N) - \log_{10}(I_H)$$

where I_N = the intensity of reflected light on the normal side, I_H = the intensity of reflected light on the hematoma side.

In summary: The Infrascanner includes three components: (1) the Scanner, (2) the Disposable Shield and (3) a Cradle. The Scanner includes a safe NIR diode laser and a silicon detector. The light to and from the laser and detector are optically coupled to the patient's head through the disposable shield optical fibers. The optical fibers are long enough to reach through hair and contact the scalp. The optical fibers are placed 4 cm apart allowing optimal detection of hematomas. The extended fiber optics eliminates the need to shave off any hair. And because the fiber optic piece is disposable it prevents cross contamination. The detected light passes through an optical NIR band-pass filter in order to minimize background light interference. Electronic circuitry is included to control laser power and the detector signal amplifier gain. The detector signal is digitized and analyzed by a single board computer, SBC, in the Scanner. The SBC receives the data from the detector and automatically adjusts the settings of the Scanner to ensure good data quality. The data is further processed by the SBC and the results are displayed on the screen. Readout of the scan provides information on the severity of a hematoma and identifies the region of the brain bleeding. A higher optical density in the scanned region indicates a larger hematoma (20).

- 11. Risk/Benefit Assessment:** There are neither any specific clinical benefits to the research participant, nor are there any direct incentives, financial or otherwise, provided to the research participant. There is no known health risk of interval, short-term use of the device.
- 12. Costs to the Subject:** No additional costs to the patient will be incurred as a result of this add-on, intraoperative research protocol.

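### The accuracy tables are not split by scalp hematoma, so they cannot show how far sensitivity and specificity depend on scalp blood, and one of the two regressions pools its opposite effects.

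*SAP*

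**What the plan says.** Protocol section 10 gives the measuring principle: "extravascular blood absorbs NIR light more than intravascular blood". Light enters and leaves through the scalp: "The optical fibers are long enough to reach through hair and contact the scalp". The reading is a left-right contrast: "The Infrascanner compares left and right side of the brain in four different areas", and "The difference in optical density (ΔOD) in each of the four symmetrical areas is calculated on a pair-wise basis".

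The SAP, under Variables, records "Scalp hematoma present: Y/N, if yes, Y/N at 8 different locations (left/right frontal/temporal/parietal/occipital"). These are the eight positions the device scans. The device result is listed only as "Positive infrascan: Y/N", with no location field.

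Analysis plan item 3 is "A 2x2 table of CT and InfraScanner results". Items 4 to 7 repeat it by quadrant, within the detection limit, by hematoma type, and by type within the limit. None has a stratum, exclusion or sensitivity analysis for scalp hematoma, and the Table 1 shell does not list it.

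Scalp hematoma is used in two logistic models:
- Statistical Analysis item 4, where the outcome is correct versus incorrect detection.
- Analysis plan item 11, where the outcome is the InfraScanner result and the listed factors end with "skin color, scalp laceration, scalp fracture, and scalp hematoma". CT status is not among the listed terms.

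The inclusion statement covers suspected head trauma with a brain CT and does not exclude patients with scalp hematoma.

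**The concern.** A scalp hematoma on one side is extravascular blood in tissue that the light has to cross, and it creates a left-right difference. It is plausible that it could make a scan positive without any intracranial contribution. If CT also shows a hematoma, the scan enters the 2x2 table as a true positive. If CT is negative, it enters as a false positive. The same mechanism therefore moves sensitivity up and specificity down.

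Aim 2 looks ahead to stand-alone use of the device where there is no CT. A reader of the results will want to know whether accuracy is similar in heads with and without scalp blood. The plan collects the variable needed to answer this but does not tabulate accuracy by it. The correct/incorrect model does not fill the gap. A scalp-driven positive is scored correct in a CT-positive patient and incorrect in a CT-negative one, and a single coefficient averages the two.

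**Working it through.** **1. The plan's own figures.** Protocol section 13(c) uses a 90% interval with half-width 1.645 × √(p(1−p)/n), largest at p = 0.5.
- n = 68: 0.0997 (stated 0.099).
- 68 / 0.13 = 523.08 (stated 523).
- 523 − 68 = 455, half-width 0.0386 (stated 0.038).

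These reproduce, apart from truncation. The SAP's final sample is 500 patients. At 13%, 500 × 0.13 = 65 are CT-positive and 435 CT-negative, with half-widths of at most 0.102 and 0.039.

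**2. Assumptions.** The documents give no frequency of scalp hematoma and no rate of scalp-driven positives. Let s be the share of patients with a scalp hematoma and q the chance that it alone turns an otherwise negative scan positive. Then:
- apparent sensitivity = Se + (1 − Se) × s × q
- apparent specificity = Sp × (1 − s × q)

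These formulas only add positives. Opposite-side scalp blood could offset an intracranial signal and symmetric scalp blood could cancel, so the sensitivity gains below are upper-side illustrations.

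**3. Range for sensitivity** (s 0.2 to 0.6, q 0.25 to 0.75). The value 0.88 is the earlier device's sensitivity within its detection limits, as quoted in both documents; the others are assumed.

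| Intracranial Se | Rise in apparent Se | Extra true positives of 65 |
|---|---|---|
| 0.88 | 0.006 to 0.054 | 0.4 to 3.5 |
| 0.70 | 0.015 to 0.135 | 1.0 to 8.8 |
| 0.50 | 0.025 to 0.225 | 1.6 to 14.6 |

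**4. Range for specificity** (Sp 0.91, the earlier device's quoted value; s 0.1 to 0.4; same q). Apparent specificity is 0.887 to 0.637, or about 10 to 119 extra false positives of 435.

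**5. The correct/incorrect model.** Take Se 0.70, Sp 0.91, s = 0.4 in CT-positives and 0.2 in CT-negatives, q = 0.5.
- Apparent sensitivity: 0.70 + 0.30 × 0.4 × 0.5 = 0.76. Apparent specificity: 0.91 × (1 − 0.2 × 0.5) = 0.819.
- CT-positive: correct with scalp hematoma 0.70 + 0.30 × 0.5 = 0.85, without 0.70. OR = (0.85/0.15) / (0.70/0.30) = 2.43.
- CT-negative: correct with scalp hematoma 0.91 × 0.5 = 0.455, without 0.91. OR = (0.455/0.545) / (0.91/0.09) = 0.08.
- Pooled: with scalp hematoma (26 × 0.85 + 87 × 0.455) / 113 = 0.546; without (39 × 0.70 + 348 × 0.91) / 387 = 0.889. OR = 0.15.

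The pooled value reflects the CT-negative majority. The rise in sensitivity cannot be seen in it.

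**6. The InfraScanner-result model.** For a positive result, the same inputs give OR 2.43 in CT-positives (0.85 against 0.70) and (0.545/0.455) / (0.09/0.91) = 12.1 in CT-negatives. Both point the same way, but their sizes differ widely, and without CT status the model reports one number for both.

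**The case against.** Sensitivity and specificity are defined as device result against CT, in head-trauma patients with no scalp exclusion. For that population the all-comer values are the right estimates, whatever caused a positive. This stands. The device section contrasts a hematoma with normal brain tissue and never mentions scalp hematoma, so a scalp effect is an inference. This also stands. The plan names scalp hematoma as a potential confounder and models it twice, and this is a pilot in which factors affecting accuracy are exploratory. That is true, but neither model recovers sensitivity and specificity by scalp status.

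Three stronger readings are tempting, and the documents do not support them:

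- **That the headline specificity is biased.** About 87% of patients are expected to be CT-negative, and there scalp-driven positives already count against the device. A lower specificity from that cause is real in this population.
- **That a single head-level scalp term would average to nothing,** because same-side blood adds to ΔOD and opposite-side blood subtracts. This needs a chosen balance, such as a 50/50 mix among CT-positives with sensitivities of 0.90 and 0.60 around 0.75. In the illustration above, the pooled odds ratio for a correct result is 0.15, far from null. The SAP also does not state how the term is coded, so head-level coding is itself an inference.
- **That positives lying over a scalp hematoma should not count as detections.** Suppose intracranial detection is 0.75, scalp hematoma is present in 20% and the trigger rate is 0.3. Apparent sensitivity is 0.75 + 0.25 × 0.2 × 0.3 = 0.765. If every positive in patients with scalp hematoma were removed, 0.2 × (0.75 + 0.25 × 0.3) = 0.165 would go, leaving 0.60. At 40% and 0.6 the figures are 0.81 − 0.36 = 0.45. That discards far more true detections than the inflation it targets.

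A same-side/opposite-side covariate is likewise undefined for the roughly 435 CT-negative patients, who have no bleed side.

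**Conclusion.** The point holds as a cheap improvement to reporting. It is not a flaw in the primary estimates. The plan collects scalp hematoma but does not report accuracy by it, and the correct/incorrect model merges two effects of opposite sign. Under the stated assumptions, the effect on sensitivity runs from below one percentage point to more than the planned ±0.10. The documents cannot say where in that range the trial lies, or whether there is any effect. The conclusion does not rest on the size. It rests on the mechanism being plausible from the protocol's own description and on the absence of any table that would reveal it.

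**What to change.** 1. Keep the overall tables as primary and unchanged.
2. In Analysis plan items 3 and 5, add sensitivity and specificity separately for patients, and for scans, with and without scalp hematoma, using Variables item 7. Give intervals at the same confidence level as the overall table. For the patient-level split, state that scalp status is taken from the assessment that classifies the patient.
3. In Statistical Analysis item 4 and Analysis plan item 11, estimate the scalp-hematoma term separately in CT-positive and CT-negative patients, or add CT status and a scalp-by-CT-status interaction. State how the term is coded.
4. If the InfraScanner result is held by side and area, add it to the variable list; item 4's quadrant tables already need it by area. Then describe, as exploratory, how many positives lie over a scalp hematoma, without reclassifying them as non-detections.

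Steps 1 to 3 need only SAP wording and a few table rows from variables already listed. Step 4 depends on data that the SAP does not list. The price is precision: if 40% of 65 CT-positives have a scalp hematoma, the groups are 26 and 39, with 90% half-widths of up to 1.645 × √(0.25/26) = 0.161 and 1.645 × √(0.25/39) = 0.132. The split results should be presented as descriptive.
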